8.5 Calculation or derivation of safety variable(s)

Adverse events

Adverse Events (both in terms of MedDRA preferred terms and CTCAE grade) will be listed individually by patient.

Any AE occurring before treatment with AZD9291 will be included in the data listings but will not be included in the summary tables of AEs.

Any AE occurring within 28 days of discontinuation of investigational product (ie, the last dose of AZD9291) will be included in the AE summaries. Any events in this period that occur after a patient has received further therapy for cancer (following discontinuation of AZD9291) will be flagged in the data listings.

A separate data listing of AEs occurring more than 28 days after discontinuation of AZD9291 will be produced. These events will not be included in AE summaries

Other significant adverse events (OAEs)

During the evaluation of the AE data, an AstraZeneca medically qualified expert will review the list of AEs that were not reported as SAEs and AEs leading to discontinuation. Based on the expert's judgement, significant AEs of particular clinical importance may, after consultation with the Global Patient Safety Physician, be considered OAEs and reported as such in the CSR. A similar review of laboratory/vital signs/ECG data will be performed for identification of OAEs.

Examples of these could be marked haematological and other laboratory abnormalities, and certain events that lead to intervention (other than those already classified as serious), dose reduction or significant additional treatment.

Safety Assessments

For change from baseline summaries for vital signs, laboratory data, LVEF, ECGs and physical examination, the baseline value will be the latest result obtained prior to the start of investigational product.

The denominator used in laboratory summaries will only include evaluable patients, in other words those who had sufficient data to have the possibility of an abnormality.

For example:

- If a CTCAE criterion involves a change from baseline, evaluable patients would have both a pre-dose and at least 1 post-dose value recorded
- If a CTCAE criterion does not consider changes from baseline, to be evaluable the patient need only have 1 post dose-value recorded

The denominator in vital signs data should include only those patients with recorded data.

8.6 Calculation or derivation of pharmacokinetic variables

Pharmacokinetic analysis of the plasma concentration data for AZD9291 and its metabolites will be performed by Quantitative Clinical Pharmacology, AZ or delegate on behalf of Quantitative Clinical Pharmacology. The actual sampling times will be used in the parameter calculations.

Where possible the following PK parameters will be determined for AZD9291 on each of the PK sampling days, using standard non-compartmental methods: maximum plasma concentration (C_{max}) or maximum plasma concentration at steady state (C_{ss max}), time to C_{max} (t_{max}) or time to C_{ss max} (t_{ss max}), area under the plasma concentration-time curve from zero to 24 hours (AUC(0-24)) or from zero to the end of the dosing interval (AUC_{ss}). In addition, the minimum plasma concentration at steady state (C_{ss min}), apparent plasma clearance at steady state (CL_{ss/F}) and extent of accumulation on multiple dosing (RAC) will be determined where possible.

C_{max}, C_{ss max}, t_{max} and t_{ss max} will be determined by inspection of the concentration-time profiles. AUC(0-24) and AUC_{ss} will be calculated using the linear up / log down trapezoidal rule. CL_{ss/F} will be determined from the ratio of dose/AUC_{ss} and accumulation ratio (RAC) will be calculated as the ratio of AUC_{ss} after multiple dosing to AUC(0-24) after single dose.

Where possible the appropriate pharmacokinetic parameters will also be determined for the metabolites of AZD9291.

The ratio of metabolite to AZD9291 will be calculated.

The plasma concentration data for AZD9291 (and the metabolites AZ5104 and AZ7550) will also be analysed using a population pharmacokinetic approach, which may include exploring the influence of covariates on PK, if the data allows. A pharmacokinetic-pharmacodynamic approach will be used to investigate the relationship between PK and selected primary, secondary and/or exploratory endpoints, where deemed appropriate. Results may be reported separately from the Clinical Study Report for the main study.

The data collected in this study may also be combined with similar data from other studies and explored using population pharmacokinetic and/or pharmacokinetic-pharmacodynamic methods. The results of any such analyses will be reported separately from the Clinical Study Report.

8.7 Calculation or derivation of QT variable(s)

The analyses of the dECG data will be performed by the designated ECG Service provider's standard operating procedures (SOPs) and Work Instructions will be used as the default methodology if not otherwise specified.

The variables to be reported from the continuous dECG measurements are RR, PQ, QRS, and QT. Summaries and analysis will be conducted using data from the global median lead.

The QT interval will be corrected for RR (the duration of a heart beat) to obtain corrected (QT_c) variables.

The general formula for QT_c that will be used is:
 $QT_c = QT / RR_b$

with the QT intervals expressed in milliseconds and the RR interval in seconds.

Different factors for b in the formula above will be used:

1. For QTcF $b=1/3$
2. For individual QT correction (QTcI), individual values of b_i will be estimated for each patient from the study data.

For the estimates of the individual-specific correction factors, the estimate of individual slopes, b_i , a fixed effects linear model for patient i , part p , and time point t will be used:

$$\log(QT_{i,p,t}) = a_{i,p} + b_i \log(RR_{i,p,t})$$

The corrected QT is then obtained by:

$$QTcI_{i,p,t} = QT_{i,p,t} / ((RR_{i,p,t})^{b_i})$$

The estimation will be based on data from the baseline day.

Additional methods of QT correction may also be applied.

The time points defined for the collection of ECG data are specified in [Table 4](#). To obtain a single value of QTcF, RR, PR, QRS and QT at each specified time point, the mean of the triplicate values at that time point will be used.

For each patient, the change-from-baseline in an ECG variable at each time point will be calculated as the difference between the mean of the replicate value at each post-dose time point and the mean of the time-matched replicate value at the corresponding baseline.

8.8 Calculation or derivation of health State utility (EQ-5D-5L)

The EQ-5D-5L index comprises 5 dimensions of health (mobility, self-care, usual activities, pain/discomfort and anxiety/depression). For each dimension, respondents select which statement best describes their health on that day from a possible 5 options of increasing levels of severity (no problems, slight problems, moderate problems, severe problems and unable to/extreme problems). A unique EQ-5D health state is referred to by a 5-digit code allowing for a total of 3125 health states. For example, state 11111 indicates no problems on any of the 5 dimensions. These data will be converted into a weighted health state index by applying scores from EQ5D value sets elicited from general population samples (the base case will be the United Kingdom valuation set, with other country value sets applied in scenario analyses). Where values sets are not available, the EQ-5D-5L to EQ-5D-3L crosswalk will be applied. In addition to the descriptive system, respondents also assess their health on the day of assessment on a visual analogue scale, ranging from 0 (worst imaginable health) to 100 (best imaginable health). This score is reported separately. The evaluable population will comprise the Full Analysis Set (FAS) population.

8.9 Methods for statistical analyses

All data will be presented for the overall full analysis set/evaluable for response set (as appropriate), and also by two cohorts defined by line of treatment; TKI treatment only / previous TKI and a platinum-based doublet chemotherapy (patients may have also received additional lines of treatment).

Descriptive statistics will be used for all variables, as appropriate. Continuous variables will be summarised by the number of observations, mean, standard deviation, median, minimum, and maximum. Categorical variables will be summarised by frequency counts and percentages for each category. Unless otherwise stated, percentages will be calculated out of the full analysis set.

Baseline will be the last assessment of the variable under consideration prior to the intake of the first dose of investigational product, except for efficacy variables. For efficacy variables, baseline is defined as the last visit prior to enrolment.

8.9.1 Analysis of the primary variable(s)

Objective response rate (ORR) by ICR in the evaluable for response analysis set will be presented together with 95% exact (Clopper Pearson) confidence intervals. Summaries of the number of patients with best response in each of the follow categories will be summarised: Complete Response (CR), Partial Response (PR), Stable Disease (SD), Progressive Disease (PD) and Non-Evaluable (NE).

The baseline patient characteristics will be summarised, including demographics, EGFR mutation type and prior anti-cancer therapy, including most recent previous treatment.

Additional summaries of ORR will be performed

- ORR by investigator assessment
- ORR summarised for both confirmed and unconfirmed responses
- ORR by EGFR mutation subtype: Exon 19 deletion/L858R/Other.
- ORR in the subgroup of patients who received TKI as last treatment prior to study start and those whose treatment prior to study start was not a TKI
- ORR at week 6 and 12 will also be summarised.

The concordance between ORR as assessed by ICR and by investigator will be presented.

8.9.2 Analysis of the secondary variable(s)

Duration of response

Duration of response in responding patients will be summarised and the number (%) of responding patients with a duration of response >3; >6; >9; >12 months will be presented. A

Kaplan Meier plot and median duration of response with 95% CI (calculated from the Kaplan Meier plot) will be presented. DCR will be summarised. DoR and DCR will be presented based on the ICR, and as a sensitivity analysis they will be present based on the investigator assessment.

Tumour shrinkage

The best absolute change in target lesion tumour size from baseline and percentage change in target lesion tumour size from baseline will be summarized using descriptive statistics and presented at each timepoint.

Tumour size will also be presented graphically using waterfall plots, to present each patient's best percentage change in tumour size as a separate bar, with the bars ordered from the largest increase to the largest decrease. Reference lines at the +20% and -30% change in tumour size levels will be added to the plots, which correspond with the definitions of progression and 'complete or partial' response respectively.

The mean and median best change from baseline in tumour size will be summarized. This will also be summarised for week 6 and week 12 data.

To assess the depth of tumour shrinkage, the proportion of patients who achieve >30%, >50% and >75% reduction in target lesions will be summarised descriptively.

Tumour shrinkage will be presented based on the primary reader ICR data, and as a sensitivity analysis they will be present based on the investigator assessment.

Progression Free Survival (PFS)

PFS will be displayed using a Kaplan-Meier plot. The number events, median (calculated from the Kaplan Meier plot), and the proportion of patients without an event at 6, 12 and 18 months summarised. PFS will be presented based on the ICR assessments, and as a sensitivity analysis PFS will be presented based on the investigator assessment.

Overall Survival (OS)

When there is sufficient data (>20 events), OS will be displayed using a Kaplan-Meier plot. The number events, median (calculated from the Kaplan Meier plot), and the proportion of patients without an event at 6, 12 and 18 months will be summarised.

As appropriate, summaries of the number and percentage of patients who have died, are still in survival follow-up, are lost to follow-up and have withdrawn consent will be presented.

HRQoL and symptoms

Time to symptom deterioration

For each of the 6 symptoms scales/items in QLQ LC13 (dyspnoea, cough, haemoptysis, chest pain, arm/shoulder pain, other pain) time to deterioration in symptoms will be presented using a Kaplan-Meier plot. Summaries of the number and percentage of subjects experiencing a clinically meaningful deterioration or death, and the median time to deterioration will be also be provided. The proportion of patients alive and free from symptom deterioration at 3, 6, 12 and 24 months will be summarized using the Kaplan-Meier estimates.

Symptom Improvement Rate

For each of the symptom scales/items in QLQ LC13, a 95% confidence interval for symptom improvement rate will be constructed using the Newcombe-Wilson method. In addition, the change from baseline at each assessment time point (in terms of proportion of patients improved, stable, and worsened as defined in Section 8.4) and the mean change from baseline scores at each time point will be summarised for all symptom scales/items from the QLQ LC13 and QLQ-C30.

Definition of clinically meaningful changes

For each functional scale in the QLQ-C30 (physical, role, emotional, cognitive, social) and for Global Health status, the change from baseline at each assessment time point (in terms of proportion of patients improved, stable, and worsened as defined in Section 8.4) and the mean change from baseline scores at each time point will be summarised.

Safety Assessments

Safety and tolerability data will be presented using summaries and descriptive statistics, as detailed in the SAP.

AEs (both in terms of MedDRA preferred terms and CTCAE grade) will be listed individually by patient. The number of patients experiencing each AE will be summarised by CTCAE grade.

Other safety data will be assessed in terms of physical examination, clinical chemistry, haematology, vital signs and LVEFs. Exposure to AZD9291 will be summarised. Time on study and AZD9291 dose delays will also be summarised.

Pharmacokinetics (PK)

PK concentration data will be summarised using appropriate summary statistics and further details will be provided in the SAP.

QTc (dECG Data)

All data ECG received will be presented in data listings. ECG summaries will be presented for patients in the QTc analysis set. Data from patients excluded from the QTc analysis set will be included in the data listings, but not in the summaries. Extra measurements (such as unscheduled or repeat assessments) will also not be included in summary tables, but will be included in patient listings.

The dECG intervals (absolute values and change from baseline) will be listed and summarised using descriptive statistics (n, mean, SD, %CV, median, minimum, and maximum). The QT/QTc outliers are defined as QT/QTc values following dosing that are greater than 450 ms or are increases from baseline greater than 30 ms. QT/QTc outliers will be highlighted in the data listings and summarised using the following categories: values that are greater than 450 ms to 480 ms or less; greater than 480 ms to 500 ms or less; and greater than 500 ms; or are increases from baseline of greater than 30 ms to 60 ms or less; and greater than 60 ms. The number and percentage of patients who meet the ECG outlier criteria at any assessment post date of first dose will be summarised.

Additionally, dECG data may be analysed together with PK data using statistical methods and PK/PD modelling; the methodology for these analyses will be described separately from this protocol and analyses will not be included in the CSR.

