5.1 Efficacy assessments

5.1.1 RECIST 1.1

All imaging assessments including unscheduled visit scans should be collected on an ongoing basis and sent to an AstraZeneca (AZ) appointed Clinical Research Organisation (CRO) to enable independent central analyses.

For both Independent Central Review (ICR) and investigator review RECIST 1.1 criteria will be used to assess each patient's tumour response to treatment and allow calculation of ORR, PFS, DCR, DoR, and assess tumour shrinkage. The RECIST 1.1 guidelines for measurable, non-measurable, target and non-target lesions and the objective tumour response criteria [CR (complete response), PR (partial response), SD (stable disease) or PD (progression of disease)] are presented in [Appendix D](#). For ORR, a visit response of CR or PR must be confirmed by a later scan conducted at least 4 weeks after the initial response is observed. See [Section 4](#) for considerations related to RECIST 1.1 assessments.

The methods used at baseline for assessment of tumour burden [CT or MRI scans of chest and abdomen (including liver and adrenal glands)] must be used at each subsequent follow-up assessment. Any other areas of disease involvement should be additionally investigated based on the signs and symptoms of individual patients. CT/MRI scan of the brain should be performed in patients with known or suspected brain metastases. The baseline assessment should be performed within 28 days of treatment start. Assessments to be performed every 6 weeks relative to first dose until objective disease progression. It is important to follow the assessment schedule as closely as possible. If scans are performed outside of the scheduled visit \pm 1 week window interval and the patient has not progressed, every attempt should be

made to perform the subsequent scans at their scheduled time points. Any other sites at which new disease is suspected should also be appropriately imaged.

If the investigator is in doubt as to whether progression has occurred, particularly with response to non-target lesions (NTLs) or the appearance of a new lesion, it is advisable to continue treatment until the next scheduled assessment or sooner if clinically indicated and reassess the patient's status. If repeat scans confirm progression, then the date of the initial scan should be declared as the date of progression.

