ORR rate is defined as the number (%) of subjects with measurable disease with at least one visit response of CR or PR that is confirmed at least 4 weeks later (according to ICR for the primary analysis). Data obtained up until progression, or last evaluable assessment in the absence of progression, will be included in the assessment of RR. However, any complete response or partial response which occurred after a further anticancer therapy was received will not be included in numerator of the ORR calculation.

In the case where a subject has two non-consecutive visit responses of PR, then, as long as the time between the 2 visits of PR is greater than 4 weeks and there is no PD between the PR visits, the subject will be defined as a responder. Similarly, if a subject has visit responses of CR, NE, CR, then, as long as the time between the 2 visits of CR is greater than 4 weeks, then a best response of CR will be assigned.

Duration of Response (DoR)

Duration of response will be defined as the time from the date of first documented response, (that is subsequently confirmed) until date of documented progression or death in the absence of disease progression, the end of response should coincide with the date of progression or death from any cause used for the PFS endpoint. The time of the initial response will be defined as the latest of the dates contributing towards the first visit response of PR or CR. If the response is not confirmed, it will not be included.

If a subject does not progress following a response, then their duration of response will use the PFS censoring time.

Disease control rate (DCR)

Disease control rate is defined as the percentage of patients who have a BoR of CR or PR or SD.

Tumour Shrinkage

Tumour shrinkage will be assessed using RECIST tumour response. The absolute change and percentage change from baseline in sum of tumour size at each assessment will be calculated. The best change in tumour size will include all assessments prior to progression or start of subsequent anti-cancer therapy.

Progression Free Survival (PFS)

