8.1 Statistical considerations

Previous text:

The data cut-off for the primary analysis of ORR will take place 3 months after the last subject enrolled, to allow opportunity for all patients to complete two RECIST follow-up assessments. At this time, DoR and safety/tolerability will also be summarised. The primary analysis CSR will report the analysis of ORR supported by duration of response, and safety and tolerability data.

Revised text:

The data cut-off for the primary analysis of ORR will take place 3 months after the last subject enrolled, to allow opportunity for all patients to complete two RECIST follow-up assessments. At this time **all efficacy, QoL, PK** and safety/tolerability will **also** be summarised **as appropriate based on the amount of data at that time**. The primary analysis CSR will report the analysis of ORR supported by **other efficacy, QoL, PK**, and safety and tolerability data.

Section of protocol affected:

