8.4 Outcome measures for analyses

Previous text:

Progression Free Survival (PFS)

PFS is defined as the time from enrolment until the date of objective disease progression or death (by any cause in the absence of progression) regardless of whether the patient withdraws from study therapy or receives another anti-cancer therapy prior to progression. Patients who have not progressed or died at the time of analysis will be censored at the time of the latest date of assessment from their last evaluable RECIST assessment.

Revised text:

Progression Free Survival (PFS)

PFS is defined as the time from **date of first dose** until the date of objective disease progression or death (by any cause in the absence of progression) regardless of whether the patient withdraws from study therapy or receives another anti-cancer therapy prior to

progression. Patients who have not progressed or died at the time of analysis will be censored at the time of the latest date of assessment from their last evaluable RECIST assessment.

Section of protocol affected:

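### Duration-of-response landmarks are planned as crude percentages of responders, so they run low wherever responders are censored at or before the landmark, chiefly beyond 9 and 12 months at the 8-month cut-off

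*Supplement*

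**What the plan says.** For DoR, protocol section 8.9.2 plans that "the number (%) of responding patients with a duration of response >3; >6; >9; >12 months will be presented". It names no estimator for these percentages, no minimum follow-up, and no rule for responders censored before a landmark. The same paragraph plans a Kaplan-Meier plot and says that "median duration of response with 95% CI (calculated from the Kaplan Meier plot) will be presented". Neither amendment changes this paragraph.

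Censoring is defined in section 8.4: "If a subject does not progress following a response, then their duration of response will use the PFS censoring time". Under the PFS definition as revised by Amendment 2, patients without an event "will be censored at the time of the latest date of assessment from their last evaluable RECIST assessment", that is, at the last scan and not at the data cut-off. Section 5.1.1 sets the scan interval: "Assessments to be performed every 6 weeks relative to first dose until objective disease progression".

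There are three analysis times. The primary cut-off "will take place 3 months after the last subject enrolled" (section 8.1, Amendment 2). The full report follows about 8 months after last enrolment, a time chosen so that responders can show more than 6 months of response. An update comes 12 to 24 months after last enrolment. For the primary cut-off, Amendment 2 adds that endpoints other than ORR are summarised only as far as the amount of data allows.

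Elsewhere in section 8.9.2 the protocol does name the estimator: the landmark proportions for symptom deterioration "will be summarized using the Kaplan-Meier estimates".

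**The concern.** A percentage of all responders treats a patient censored at 5 months, still in response, exactly like a patient who progressed at 5 months. With staggered entry, the figure then mixes how long responses last with how long ago patients enrolled.

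In a single-arm trial, DoR is the main support for the response rate. Tabulated landmarks that fall below the Kaplan-Meier curve in the same report would confuse readers. They would also rise from one report to the next with no change in durability. Section 1.5 allows the two cohorts to close at different times, and all summaries are given by cohort, so a cohort that closes earlier could look more durable through longer follow-up alone.

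**Working it through.** **Inputs from the documents.** Scans every 6 weeks from first dose; censoring at the last evaluable scan; response confirmed at least 4 weeks later, so at the next 6-weekly scan; cut-offs 3, 8 and 12–24 months after last enrolment; landmarks 3, 6, 9 and 12 months.

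**Assumptions not in the documents.** Uniform accrual over A = 4, 6 or 9 months; exponential time from response to progression with median m = 8 or 12 months; 80% of first responses at week 6 and 20% at week 12; no missed scans or dropout; 1 month = 4.348 weeks.

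**Step 1: the plan's own figure.** The 8-month cut-off is meant to show DoR above 6 months. In calendar time, 8.00 − 1.38 (first scan at 6 weeks) = 6.62 months, so the figure reproduces. Under the plan's censoring rule, 8 months is 34.8 weeks, the last scan is at week 30, and the last-enrolled patient's longest censored DoR is 30 − 6 = 24 weeks = 5.5 months, short of 6. The same arithmetic gives 1.4 months at the 3-month cut-off, 9.7 at 12 months and 22.1 at 24 months.

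**Step 2: formula.** With administrative censoring only,

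crude % beyond L = P(DoR > L) × F,

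where F is the share of responders whose scan schedule can reach beyond L before the cut-off. Kaplan-Meier estimates P(DoR > L).

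**Step 3: P(DoR > L).** On a 6-week grid, DoR beyond 6 months (26.1 weeks) means no progression by 24 weeks (5.52 months) after response. Confirmed responders are already progression-free at 6 weeks (1.38 months). So:
- L = 3: 0.5^((2.76 − 1.38)/m) = 89% (m = 8) or 92% (m = 12)
- L = 6: 0.5^((5.52 − 1.38)/m) = 70% or 79%
- L = 9: 0.5^((8.28 − 1.38)/m) = 55% or 67%
- L = 12: 0.5^((11.04 − 1.38)/m) = 43% or 57%

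**Step 4: F.** To be counted beyond 6, 9 or 12 months, a responder needs a scan 30, 42 or 54 weeks after response. For a week-6 response that is 8.28, 11.04 or 13.80 months after first dose; for a week-12 response, 9.66, 12.42 or 15.18 months. With cut-off c and required time t, the eligible share is 1 − (t − c)/A, held between 0 and 1.

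Examples at c = 8:
- L = 6, A = 4: F = 0.8 × (1 − 0.28/4) + 0.2 × (1 − 1.66/4) = 0.86. With m = 8, crude = 0.86 × 70% = 60% against 70%.
- L = 9, A = 4: F = 0.8 × (1 − 3.04/4) + 0.2 × 0 = 0.19. With m = 8, crude = 0.19 × 55% = 11% against 55%.
- L = 9, A = 9: F = 0.8 × (1 − 3.04/9) + 0.2 × (1 − 4.42/9) = 0.63. With m = 12, crude = 0.63 × 67% = 42% against 67%.

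**Step 5: all scenarios.** A simulation of 200,000 patients under the same assumptions agrees with the formula to about a point at the 8-, 12- and 24-month cut-offs. The 3-month row is from the simulation alone, because some late responses are not yet confirmed by then. Entries are crude % against true %, over all A and m.

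| Cut-off after last enrolment | >3 months | >6 months | >9 months | >12 months |
|---|---|---|---|---|
| 3 months | 29–65 v 89–92 | 0–31 v 70–79 | 0–6 v 55–67 | 0 v 43–57 |
| 8 months | equal | 60–74 v 70–79 (4–11 low) | 11–42 v 55–67 (20–54 low) | 0–19 v 43–57 (29–57 low) |
| 12 months | equal | equal | about 1 low | 21–44 v 43–57 (10–30 low) |
| 24 months | equal | equal | equal | equal |

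The share of responders censored at or before the landmark at the 8-month cut-off is 0% (>3), 4–11% (>6), 22–58% (>9) and 36–70% (>12). Kaplan-Meier matched the true rate wherever it could be estimated. At the 8-month cut-off with 4 months' accrual it cannot be estimated at 12 months, whereas the crude summary would print 0%.

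**The case against.** The strongest reply is that censoring is already handled. The same paragraph plans a Kaplan-Meier curve and median with confidence interval, and any landmark can be read off that curve. A count beside it is descriptive. The landmark the 8-month cut-off was timed for, 6 months, is only 4 to 11 points low, and the later update removes most or all of the bias. The error runs against the drug, affects neither the response rate nor any decision rule, and its size rests on assumed accrual and durability. The SAP is not shown and may specify the estimator.

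Much of this stands and limits the point. It does not remove it. The protocol itself specifies the summary, and it names Kaplan-Meier where it means it, for the median and for the symptom landmarks. Reading values off a curve gives no tabulated estimate or interval.

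Four stronger readings are tempting but unsupported:
- **That every censored responder counts as a failure.** Only those censored at or before the landmark do; those censored later count as successes.
- **That most responders are censored before 6 months at the 8-month cut-off.** The share is 4–11% in these scenarios.
- **That the very low figures at the 3-month cut-off will be published.** Amendment 2 ties those summaries to the amount of data, though it sets no rule for landmarks.
- **That PFS and OS share the defect.** For PFS the text says "the proportion of patients without an event at 6, 12 and 18 months summarised", in the same sentence as a Kaplan-Meier median; the OS wording is parallel. That is ambiguous, not plainly crude, and is not part of this point.

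**Conclusion.** The point holds for the DoR landmark percentages only. Followed as written, section 8.9.2 understates durability wherever responders are censored at or before the landmark. The direction follows from the censoring rule and the timing of the cut-offs; the size depends on accrual and median DoR, which the documents do not give. Under the stated assumptions the shortfall matters most at the 8-month cut-off: modest beyond 6 months, large beyond 9 and 12. A reader should not infer that durability is understated at every cut-off. The percentages are sound beyond 3 months at 8 months, beyond 3 and 6 months (and within about a point beyond 9) at a 12-month update, and at all landmarks at 24 months. The Kaplan-Meier plot and median are not in question. It is a correction worth making to a supporting summary and does not touch the primary analysis.

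**What to change.** In section 8.9.2, or in the SAP if it does not already do so, define the 3-, 6-, 9- and 12-month DoR rates as Kaplan-Meier estimates with 95% confidence intervals. Give the number at risk at each landmark. Show an estimate only where follow-up reaches the landmark, and otherwise mark it as not estimable instead of printing a low or zero percentage. If raw counts are kept, label them as observed to date. Apply the same rule to the cohort tables and to the investigator-assessed sensitivity analysis.

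The cost is wording and table shells. The Kaplan-Meier analysis is already planned and no new data are needed.
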